There is significant variability in response to any given rehabilitation intervention, and the neural bases of this variability are not well understood. Electroencephalography (EEG) is a research tool with an established history of clinical application following TBI (Rapp et al., 2015; Schmitt & Dichter, 2015). Previous reports of mild to moderate TBI have suggested alterations in the theta (4-8 Hz) and alpha (8-13 Hz) ranges (Thornton & Carmody, 2009). Given its availability in clinical settings, and utility in measuring the effects of attention and working memory (Luck et al., 2000), we propose to examine the neurophysiologic underpinnings of behavioral responses to training using well-validated event-related EEG markers, and novel application of EEG network connectivity measures to resting state data. In a related example, EEG markers for Attention-Deficit Hyperactivity Disorder (ADHD) suggested that processing deficits in the encoding and maintenance stages of working memory (WM) are differentially explained by variance in theta and alpha (Lenartowicz et al., 2014). Application of these methods to understand and even predict treatment outcomes could help direct interventions, save time, and improve patient quality of life. Better understanding the neural bases of functional improvements may help guide intervention development by providing new markers for feedback or targets for electrical modulation.

We will use a novel combination of neurocognitive training and two categories of EEG data for these investigations. (a) Event related changes in brainwaves can dissociate components of working memory into discrete processes that are targeted by training (attention, encoding, maintenance). We will examine EEG with WM load under distraction pre- and post-training, and test whether these markers help to explain neural bases of variability in behavioral changes with training. We predict that training-induced changes in

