**Pre- and Post-Training EEG:** Participants will attend testing sessions pre- and post-training. The first phase of each session measures several minutes of resting state brainwaves for use in connectivity modeling (Langer et al., 2013). Participants will complete a brief assay of self-regulation, with instructions to relax and focus on the cycle of breathing, re-directing attention if the mind wanders, as in our prior fMRI study (Arnemann et al., 2015). In the second phase, participants will perform our well-validated working memory dual task while EEG is recorded and averaged using standard methods. EEG time-frequency analyses will target the theta and alpha bands based on prior studies (Thornton & Carmody, 2009). This experiment is ideal for use in evaluating potential neural mechanisms of our targeted training, because of its sensitivity to working memory load and distractions. Data will be collected by staff in [name] lab, and EEG analysis carried out by [name], who has experience describing EEG markers and evaluating novel training approaches in clinical populations (Pineda et al., 2014).

**ERP Recording:** Continuous EEG will be recorded from 64 scalp electrodes and two electrodes placed on the left and right mastoids using the ActiveTwo Biosemi electrode system. Four electrodes placed laterally and below both eyes will record blinks and eye movements. The EEG will be sampled at 512 Hz. Biosemi uses a “common mode sense” active electrode and “driven right leg” passive electrode to form a feedback loop that serves as the “ground” electrode. All signals will be recorded using ActiView software.

**ERP Data Analysis:** Off-line analysis will be completed using Brain Vision Analyzer software. Data will be re-referenced to the average of the mastoid electrodes and bandpass filtered from 0.1 to 30 Hz (48 dB/octave). The EEG will be segmented for each trial beginning 100 ms pre-stimulus and extending to 900 ms post-stimulus onset. EEG will be corrected for blinks using the Gratton procedure; artifacts exceeding 150  $\mu$ V will be rejected. Segments will be baseline corrected and averaged with similar trials. ERPs will be

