quantified by computing mean amplitudes in defined latency windows relative to a 100 ms pre-stimulus baseline. The primary measure will be the ERP “old/new effect” elicited during memory retrieval, time-locked to probe onset. This will be quantified by subtracting mean amplitude for Old – New probes (300-500 ms post-stimulus) at midline electrodes (Honzel et al., 2014).

**EEG Time-Frequency and Network Analysis:** Off-line analysis for resting state and dual task data will be performed in the EEGLAB Matlab toolbox (Delorme & Makeig, 2004). Data will be filtered with bandpass limits of 0.1 to 55 Hz using a standard FIR filter and re-referenced to the average of mastoid electrodes. Periodic artifacts, such as eyeblinks, will be removed using the Infomax Independent Component Analysis (ICA) algorithm. Remaining data will be further band filtered into four frequency bands (theta: 4-8 Hz, alpha: 8-13 Hz, beta: 15-30 Hz, & gamma: 30-55 Hz), and power envelope and phase angle will be extracted with a Hilbert transform.

Resting state connectivity will be calculated over two second epochs using a graph theoretical approach comparing each pair of electrodes in each frequency band, based on correlation of band power changes, and degree of phase coherence. *As we are working with resting state data, we have no a priori hypothesis about directionality of information flow. Therefore, correlations of these measures will suffice (Bastos & Schoffelen, 2016), thereby decreasing computation demands.* Spurious connectivity will be corrected by eliminating neighboring electrode connections and ignoring electrode pairs with 0 degrees of phase lag. Remaining electrode pairs will be adjusted to a common threshold to control number of network connections across patients. From these binarized connectivity matrices, modularity and characteristic path length (CPL) will be calculated using the Matlab toolbox, EEGNET (Hassan, et al. 2015). Time-frequency responses to dual task conditions will be calculated using Hilbert transformed data, epoched and averaged over the same time window and baseline as ERP analysis.

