## Experimental Design

### EEG of Working Memory with and without a secondary attention task

Rationale: Previous studies in this population have shown a decline in WM performance that is exacerbated by increased task demands (Honzel et al., 2014). An established EEG marker of WM retrieval, the ERP old/new effect, indexed this impairment. Another EEG marker, frontal midline theta, is a sensitive correlate of working memory load (Gevins et al., 1997) that exhibits increases in power during cognitive demands for WM (Onton et al., 2005). This experiment will test the hypotheses that (a) patients will show changes in these markers with training; and (b) the EEG changes will explain variability in behavioral changes as measured by the operation span score and the attention/executive function composite score. We will examine EEG and behavioral performance on the Sternberg WM task alone and when the flanker interference task is performed during the maintenance period. Preliminary results from the training intervention suggest that improvements in working memory, attention, and executive functions can occur. Temporally sensitive EEG measures may elucidate the neural correlates of these changes, and help to explain individual differences in treatment response.

Experimental Design: The study will use the methods of Honzel et al. (2014), briefly described below.

Single-Task Condition (Sternberg Memory Task): Participants will be asked to remember either one or four consonants. After an 8500 ms delay, another consonant will be presented (probe). Participants respond with a button press to indicate whether the probe was part of the previous memory set (old) or whether the

probe was not part of the memory set (new).

**Single-Task Condition (Arrow Flanker Task):** Participants will be instructed to respond with a button press to indicate whether the central arrowhead points to the left or the right. Flanking arrows, positioned either above, below, or both above and below the central arrow, can point in either the same (congruent) direction (40% of trials) or different (incongruent) direction (60% of trials). Each flanker stimulus is presented for 200 ms, with the next trial beginning 300 to 500 ms after a response was made.

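### The window and baseline set for task time-frequency power leave most of the maintenance delay unmeasured against a baseline outside it, although the plan claims to locate training effects by working memory stage

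*Combined protocol and SAP*

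**What the plan says.** The rule is in Research Design and Methods, under EEG Time-Frequency and Network Analysis: Hilbert-transformed data for the dual task conditions are "epoched and averaged over the same time window and baseline as ERP analysis". ERP Data Analysis defines that window: "The EEG will be segmented for each trial beginning 100 ms pre-stimulus and extending to 900 ms post-stimulus onset", with amplitudes taken relative to the 100 ms before the stimulus. The only time-lock named is for the primary ERP measure, the old/new effect "elicited during memory retrieval, time-locked to probe onset", which is formed by "subtracting mean amplitude for Old – New probes". The plan gives time-frequency power no lock, no delay-period window and no pre-trial baseline of its own.

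The delay is long compared with that window. In the single Sternberg task the probe follows after 8,500 ms. In the dual task nine flanker trials fill the delay. The first starts 300–500 ms after the memory set, the flanker trials are response-paced ("with the next trial beginning 300 to 500 ms after a response was made"), and the probe comes 500 ms after the last one.

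Predicted Results in the working memory section states that the EEG can place training effects in encoding, maintenance and/or retrieval. It takes its theta rationale from ADHD work in which theta rose during maintenance. Background and Significance makes stage separation a stated purpose: "Event related changes in brainwaves can dissociate components of working memory into discrete processes that are targeted by training (attention, encoding, maintenance").

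**The concern.** A one-second epoch with an immediately preceding baseline suits a transient potential after a probe. It does not suit band power that may change for the whole of a delay lasting many seconds. If the baseline itself lies in the delay, a lasting change in maintenance power is present on both sides of the comparison and drops out.

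Frontal midline theta is one of the markers in the experiment's two hypotheses (change with training, and explaining behavioural variability). The resting-state section then uses task theta and alpha power as something to be predicted. If the maintenance level is not measured, finding no maintenance effect would say little. With the lock unstated, the choice of lock could also be made after the data are seen.

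**Working it through.** **Inputs from the plan:** epoch −100 to 900 ms; baseline 100 ms; single-task delay 8,500 ms; nine flanker trials; first flanker 300–500 ms after the set; gap 300–500 ms after each response; probe 500 ms after the last flanker trial.

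**Assumptions:** the sentence on dual task conditions covers the whole experiment, single-task Sternberg included; flanker reaction time (RT) is 400–700 ms; dual-task timing runs from set offset; a flanker trial ends at its response. Set display time D and the inter-trial interval are not given.

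**Single task, share of the delay inside the epoch**
- Probe lock: 100/8,500 = 1.2%, and all of it is baseline.
- Memory-set lock: (900 − D)/8,500. D near 0 gives 10.6%; D = 500 ms gives 400/8,500 = 4.7%; D of 900 ms or more gives 0%.
- Both locks together leave at least 8,500 − 900 − 100 = 7,500 ms, or 88%, outside any epoch.

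**Dual task.** Delay = first gap + 8 × (RT + gap) + RT + 500.
- Shortest: 300 + 8 × 700 + 400 + 500 = 6,800 ms. Longest: 500 + 8 × 1,200 + 700 + 500 = 11,300 ms.
- Probe lock: 100/11,300 = 0.9% to 100/6,800 = 1.5%, again all baseline.
- Set lock: at most 900/11,300 = 8.0% to 900/6,800 = 13.2%. For D = 500 ms: 400/11,300 = 3.5% to 400/6,800 = 5.9%.
- Flanker lock: the nine epochs together span 6,600/6,800 = 97% to 9,000/11,300 = 80%. Every baseline lies inside the delay. With power raised by a factor g throughout, the ratio of window to baseline is g/g = 1. In simulation a sustained 20% theta rise was estimated as 0.0–0.1%.

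**Old-New contrast of power.** A probe's old or new status does not exist before the probe, so this contrast cannot carry a maintenance effect. It also largely protects retrieval: a simulated delay-only change moved the contrast by at most 6% of its own size, without changing its sign.

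**Probe lock without an Old-New contrast (illustration only).** The simulation assumed 1/f noise at 512 Hz, a 20% power rise, an 8.5 s delay, four 4–8 Hz filters and 6,000 trials.

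| True change | True value at retrieval | Estimate by division | Estimate by subtraction |
|---|---|---|---|
| Delay and retrieval | 20% | about 0% | about 0% |
| Delay only | 0% | −11.7% to −13.0% | −13.4% to −15.0% |
| Retrieval only | 20% | +12.5% to +13.9% | +13.2% to +14.7% |

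A second run with 3,000 trials agreed to within about 0.3 points.

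**The case against.** The best defence is that the plan promises event-related changes occurring during maintenance, not a level held through the delay. ERP Data Analysis says only pre-stimulus, so nothing confines segmentation to the probe. Two readings then reach maintenance.

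- Flanker-locked responses, compared by set size and before versus after training, are changes within the dual-task delay.
- A set-locked epoch has its baseline outside the delay and, if the set is short, its tail measures early maintenance. In a simulation with assumed sets of 200 and 500 ms, a 20% rise starting at set offset was estimated at 18.1–19.2% between set offset and 900 ms.

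Both points stand. A reader might infer that the plan cannot see maintenance at all; the documents do not support that. What remains is that the set lock stops by 900 ms, while the flanker lock removes the sustained level and has no counterpart in the single Sternberg task.

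The plan also says it uses the methods of a cited study, which may give the set duration, the inter-trial interval and other locks. That could settle some of the unknowns, but the window and baseline are stated in this plan.

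Finally, the theta and alpha prediction is not tied to a stage, no maintenance test is specified, and the study is called a pilot. This limits the weight of the point; it does not remove the mismatch between the stage claim and the analysis.

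**Conclusion.** The point holds in a limited form and should be corrected before the time-frequency analysis. Under each lock considered, the stated window and baseline fail to measure most of the delay against a baseline outside it. The best case is the set lock: at most 10.6% of the single-task delay and, at the assumed reaction times, 8–13% of the dual-task delay. These shares fall to zero if the set lasts 900 ms or more.

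The dual-task figures rest on the assumed reaction times. The single-task figures rest on reading the sentence as covering the whole experiment. If it covers the dual task alone, the conclusion still holds there, and single-task power has no stated window.

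Two stronger inferences are not supported. One is that a maintenance effect will show up as a retrieval effect of opposite sign. That needs a probe lock and no Old-New contrast, and the plan settles neither. The other is that the main results are undermined. Encoding and retrieval remain open to study with set and probe locks, the general theta and alpha prediction remains testable, and the primary ERP old/new measure is unaffected.

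**What to change.** For time-frequency power only, replace the clause that borrows the ERP window and baseline with three named epochs:

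1. Encoding, locked to the memory set.
2. Maintenance, averaged over the delay (response-paced, so of variable length, in the dual task).
3. Retrieval, locked to the probe.

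Analyse log band power per stage without a within-delay baseline. Alternatively, refer all three epochs to one baseline before the memory set, if the inter-trial interval allows. That baseline should be longer than 100 ms, which holds only 0.1 × 4 = 0.4 to 0.1 × 8 = 0.8 of a theta cycle, and it should end early enough that filter smearing from the set does not reach it. State whether power is analysed per condition or as an Old-New contrast, whether any baseline is subtracted or divided out, and whether the rule covers the single task. If no delay epoch is added, limit the stage claim in Predicted Results to encoding, retrieval and, if the set is short enough, early maintenance. Keep −100 to 900 ms for the ERP.

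The cost is wording and re-epoching: "Continuous EEG will be recorded from 64 scalp electrodes", so no new data are needed. The downsides are more artifact loss in longer epochs, flanker and button-press activity mixed into dual-task maintenance power, and possible drift between a pre-set baseline and a probe about 7–11 s or more later. In simulation, the SD of retrieval minus baseline, in units of mean power, was 0.89–0.94 with the pre-set baseline against 1.01–1.03 with the planned one at a per-trial log-power drift SD of 0.3. At a drift SD of 0.5 the pre-set baseline was the noisier, at 1.11–1.13. Unbaselined log power avoids that dependence.

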## Research Design and Methods

**Participants:** The participants will be Veterans with history of TBI:  $n = 20$  will undergo the training intervention, and  $n = 20$  will participate in repeated testing without intervention. Inclusion criteria: Veterans, ages 21 to 55, with a history of TBI (as defined by the American Congress of Rehabilitation Medicine and VA, with reported plausible mechanism of head injury, loss of consciousness with some period of post-traumatic alteration in cognition), in the chronic, stable phase of recovery ( $>6$  months from injury), with residual cognitive complaints (Neurobehavioral Symptom Inventory, cognitive subscale  $>9$ ). Participants will be on stable psychoactive medications ( $> 30$  days); able and willing to participate in EEG, training and, assessments. *Common mental health comorbidities present amongst OEF/OIF/OND Veterans, such as depression and PTS (Carlson et al., 2011; Carter, 2014), will be permitted in order to address realistic aspects of recruitment (i.e. it would be unrealistic to expect a sample of 'pure TBI' amongst current generation combat Veterans) as well as a practical goal of intervention work in addressing needs of Veterans. However, participation will be limited to Veterans reporting PTS and depression symptoms below clinical thresholds (see self-report questionnaires section for more details: PCL-5 scores  $< 38$ , Weathers et al., 2013; BDI-II scores  $< 19$ ; Homaifar et al., 2009).* Exclusion criteria: Severely apathetic/abulic, aphasic, or other reasons for being unable or unwilling to participate with the training tasks; severe cognitive dysfunction; history of neurodevelopmental abnormalities; ongoing illicit drug or alcohol abuse (AUDIT $>8$ ); schizophrenia; bipolar disorder; history of other neurological disorders; current medical illnesses that may alter mental status or disrupt participation in the study; active psychotropic medication changes. There will be no restriction in regard to gender, race and socioeconomic status.

**Study design and participant flow.** Participation in the proposed study will span approximately 10-12 weeks. Participants will be recruited via IRB-approved methods, and interested candidates will undergo preliminary screening ( $\sim 1$  hr phone interview + VA records review). Eligible participants will be invited to enroll and provide informed consent approved by the IRB of VA Northern California.

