Baseline assessments of cognitive status and functioning, as well as EEG, will be conducted in weeks 1-2. Time commitment for baseline assessments is approximately 4-5 hours. Participants will then be assigned to (a) active training or (b) no training conditions in a pseudo-random order, matched across key demographic variables. The no training condition will serve to assess changes to EEG and other measurements with repeated testing in the absence of active training. This will lay a foundation for future studies that will incorporate an active comparison intervention.

Participants in active training will complete seven training sessions in weeks 3-10. Training sessions last 2 hours, and participants are requested to complete approximately 2.5 hours of additional skill practice over the course of each week outside of session (total  $\sim 4.5$  hours per week). The same overall training time will be targeted ( $\sim 32$  hours) for all individuals, although the training schedule will accommodate variations in individuals' schedules and availability over the course of  $\sim 8$ -10 weeks to maximize engagement. In the 2 weeks after training concludes, participants will complete a second round of assessments ( $\sim 3$ -4 hrs). Participants will be compensated \$20/hr for their time during the assessment portions of the study as well as for their travel expenses at \$0.55/mile for travel greater than 20 miles to and from the study site.

Enrollment will begin within 3 months of the initiation of the grant period, and continue through month 21. Data will be checked and pre-processed on a rolling basis and final analyses and reports will be completed in months 22-24.

**Training Intervention:** Training follows a manualized protocol, with seven in-person two-hour sessions (Loya et al., 2014; Rodriguez et al., 2014) and instructions to practice skill use while playing the Startup-to-CEO game for 30 minutes/day, five times per week, and to practice skill use within the context of their daily life. Game scenarios are utilized to highlight contexts where goal-directed functioning is susceptible to disruption and where skill use might be helpful. They further help facilitate discussions about skill application in personal life. In addition, twice weekly semi-structured phone check-ins are conducted to provide motivational support and reinforce skill use.

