**Sample Size Calculation:** We powered the study based on prior group differences (mtBI/PTS vs. Controls). We used data from the Sternberg task (Honzel et al., 2014) to obtain an estimate of the standard deviation of the ERP old/new effect, and expected effect size based on a mixed effects ANOVA (subject as random effect) with group as the sole explanatory variable. To estimate sample size, we used the two sample *t* test as an approximation to the mixed effects ANOVA and used the method of variance inflation to account for the additional subject factors (Hsieh et al., 2003). We powered based on the primary experimental question at 80% and will control false discovery rate at 5% (Benjamini & Hochberg 1995) at the time of analysis for tests of other design and subject factors. The Sternberg data showed a mean difference between the patient and control groups of -1.097 with residual error of 0.956 from the mixed effects ANOVA. Using these values in a two-sample *t* test for mean difference, to obtain 80% power we need a sample size of 13 per group. *This pilot study will allow us to collect data to inform power calculations for future studies.*’

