**Dual-Task Condition (Sternberg Memory Task + Arrow Flanker):** Participants will be required to perform the arrow flanker task during the delay interval of the Sternberg memory task. Nine flanker trials begin 300 to 500 ms following the presentation of each memory set. The stimulus parameters are the same as for the single-task flanker. The Sternberg probe is then presented 500 ms following the final flanker trial, and participants respond to indicate whether this item was in the previous memory set.

**Statistical Analysis:** The ERP old/new effect will be analyzed using a mixed effects ANOVA controlling for task (single, dual), set size (one, four), and time point (pre, post). The primary neuropsychological outcome measures will be included in the models as appropriate to assess changes from pre- to post-training. To examine the effects of repeated testing, differences in ERP mean amplitudes between patient groups (trained, untrained), task, and set size will be also be tested using a separate mixed effects ANOVA to control for random effects due to subject. Pre/post differences in Sternberg WM accuracy will be tested using a hierarchical generalized linear model. Time-frequency responses will be analyzed with the same mixed and linear models, with separate calculations for each frequency band, and a repeated measures model including all frequency bands.

**Predicted Results:** We predict that Veterans who show cognitive gains with training (based on neuropsychological measures) will show an increase in the ERP old/new effect in the dual task condition. Additionally, as prior work has shown that WM impairment in ADHD is characterized by decreased levels of alpha power during encoding, and compensatory increases in theta during maintenance (Lenartowicz, et al. 2014), we predict that cognitive gains will be reflected by changes in theta and alpha power over frontal scalp. Importantly, we can determine with precise temporal resolution whether the neural manifestations of training improvements occur during WM encoding, maintenance, and/or retrieval. Additional analyses will determine whether these EEG markers can predict which patients will improve with training.

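### The 80% power claimed for the primary question belongs to a prior patient-versus-control difference that this trial does not test; power for change with training is not given

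*Combined protocol and SAP*

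**What the plan says.** Under Research Design and Methods, the Sample Size Calculation paragraph gives its basis as "We powered the study based on prior group differences (mtBI/PTS vs. Controls"). The effect size comes from a mixed effects ANOVA "with group as the sole explanatory variable": a mean difference of -1.097 and a residual error of 0.956, leading to 13 per group. The same paragraph states "We powered based on the primary experimental question at 80" per cent. It closes by calling the study a pilot that will inform later power calculations.

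The trial itself is different. The Participants paragraph enrols 20 Veterans with TBI for training and 20 more who "will participate in repeated testing without intervention". No group without TBI is enrolled. In the working-memory EEG section, hypothesis (a) is that "patients will show changes in these markers with training". Under Statistical Analysis there, a model for the ERP old/new effect comes first; the plan says that it "will be analyzed using a mixed effects ANOVA controlling for task (single, dual), set size (one, four), and time point (pre, post"). A separate model compares the arms: "To examine the effects of repeated testing, differences in ERP mean amplitudes between patient groups (trained, untrained").

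**The concern.** A power figure belongs to one contrast, with one effect size and one variance. The figure here is for a cross-sectional difference between patients and controls. The trial asks about change with training, either as trained versus untrained change or as pre/post change in the trained arm. Both depend on the size of the training effect and on the SD of change. The plan gives neither for the ERP old/new effect.

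Two things are at stake. A reader who takes 80% at face value may read a null result as evidence against a training effect when the trial had little chance of finding one. The choice of contrast also affects interpretation as well as power. The within-arm comparison looks better powered but cannot separate training from repeated testing. That is why the second arm exists: "The no training condition will serve to assess changes to EEG and other measurements with repeated testing in the absence of active training".

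**Working it through.** **Inputs from the plan.** Mean difference 1.097 (absolute value) and residual error 0.956 (Sample Size Calculation); 20 per arm (Participants).

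**Assumptions.**
- Two-sided alpha 0.05. The plan gives 5% only as a false discovery rate for other tests.
- Equal SD before and after, with 0.956 treated as the single-visit SD, as the plan does.
- Pre-post correlation r = 0.3, 0.5, 0.7 or 0.8.
- No attrition unless stated.

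All power figures use the noncentral t distribution.

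**Step 1: the plan's own figure.** d = 1.097/0.956 = 1.147. A two-sample t test has 76.6% power at 12 per group and 80.1% at 13. The stated 13 reproduces. At 20 per group the same patient-control contrast would have 94%.

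**Step 2: convert to change.** SD of change = single-visit SD × √(2(1 − r)). The SD of change equals the single-visit SD only when r = 0.5. So the 94% carries over to a between-arm comparison of change only if training closes the whole gap and r is 0.5. The plan states neither.

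**Step 3: detectable effect at 80% power.**
- Between arms, 20 versus 20: 0.909 SD of change.
- Within the trained arm, n = 20, paired: 0.660 SD of change.
- As a share of the gap: detectable effect × √(2(1 − r))/1.147. For r = 0.5, between arms: 0.909 × 1/1.147 = 0.79.

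**Step 4: power for assumed training effects.** Half the gap is 1.147/2 = 0.574 single-visit SD. The standardised effect is 0.574/√(2(1 − r)) for change scores and 0.574/√(1 − r²) with baseline adjustment.

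| | r = 0.3 | r = 0.5 | r = 0.7 | r = 0.8 |
|---|---|---|---|---|
| Between arms: detectable share of gap | 94% | 79% | 61% | 50% |
| Between arms: half-gap power, change score | 32% | 42% | 63% | 80% |
| Between arms: half-gap power, baseline-adjusted | 46% | 53% | 70% | 84% |
| Between arms: whole-gap power, change score | 85% | 94% | >99% | >99% |
| Within arm: detectable share of gap | 68% | 58% | 45% | 36% |
| Within arm: half-gap power | 54% | 68% | 88% | 97% |

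**Step 5: precision.** The 95% confidence-interval half-width, in SD of change:
- Between arms: t(38, 0.975) × √(2/20) = 2.024 × 0.316 = 0.64.
- Within arm: t(19, 0.975)/√20 = 2.093/4.472 = 0.47.

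**Step 6: attrition.** The plan states no allowance. With an assumed loss of 10% or 20% (18 or 16 completers per arm), the between-arm detectable effect rises from 0.91 to 0.96 or 1.02 SD of change.

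**The case against.** The plan does not hide its source. It says the difference is between patients and controls, and it calls the study a pilot. A pilot need not have 80% power, and borrowing a prior gap as a planning value is a weak assumption rather than a slip in calculation. On that value, 20 per arm is comfortable: at least 85% between arms for r of 0.3 or more. The half-gap case is an illustration with no support in the documents. Pre/post is also arguably primary, since that model comes first and the group model is described as separate.

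Much of this is fair, and it limits the point to the power claim. It does not rescue that claim. Disclosing the source and calling the study a pilot do not withdraw the statement that the primary question has 80% power. The whole-gap case assumes that training fully removes the patient-control difference, which the plan never argues; even then, between-arm power is 71% at r = 0. The order of the models hints at pre/post, but the text does not call either contrast primary or say whether the pre/post model is confined to the trained arm.

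One caution on the figures also stands. The value 0.956 is the residual error in the sample size paragraph but Cohen's d for the dual task in Preliminary Studies (item 4). If it is really d, half-gap between-arm power falls to 24%, 31%, 48% and 64% for the same correlations. The figures in SD-of-change units (0.91, 0.66, 0.64, 0.47) do not depend on it.

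**Conclusion.** The concern holds. The arithmetic behind 13 per group is right, but the 80% belongs to a contrast that the trial does not contain. Enrolling 20 rather than 13 per arm does not mend this, because the missing quantities are the training effect and the variance of change. Power for the trial's own question is unknown. Over the assumed correlations of 0.3 to 0.8, it runs from 32% (half gap, between arms, change score) to over 99% (whole gap), so it may be above or below 80%. The power percentages rest on the assumed alpha, correlations and training effects, and on reading 0.956 as the single-visit SD. The detectable effects and interval half-widths in SD of change need only the alpha and 20 completers per arm. The design and data remain usable; the power statement should be corrected.

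**What to change.** In the Sample Size Calculation, remove the claim that the primary question has 80% power and say that 13 per group refers to the prior patient-control difference. Name one primary contrast for the ERP old/new effect: trained versus untrained change, or pre/post change within the trained arm. If the latter, acknowledge that it cannot separate training from repeated testing.

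For the chosen contrast, report:
1. the detectable effect at 20 per arm (0.91 SD of change between arms, or 0.66 within arm);
2. power over a stated range of training effects and pre-post correlations;
3. the expected 95% confidence-interval half-width (about 0.64 SD of change between arms, or 0.47 within arm).

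Say that these are before attrition, and that the pilot's purpose is to estimate the training effect and the variance of change. Check against the source whether 0.956 is an SD or a standardised effect before building the power table on it.

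The cost is one rewritten paragraph, one named contrast, and a power statement that is less favourable or openly uncertain. It needs no extra participants or measurements.
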